12.1.5. Serious Adverse Event

An SAE is any AE that results in any of the following outcomes:

IMGC936 ImmunoGen, Inc Clinical Study Protocol: IMGC936-0901 Amendment 3 29 March 2022

- Death
- Is life-threatening
- Requires inpatient hospitalization (excludes 23-hour hold for observation, admission to hospice or nursing home, respite care, outpatient surgery, social admission, or admission for elective/preplanned surgery)
- Requires prolongation of existing hospitalization
- A persistent or significant disability or incapacity or substantial disruption of the ability to conduct normal life functions
- A congenital anomaly or birth defect
- Important medical events that may not result in death, be life-threatening, or require
 hospitalization may be considered SAEs when, based upon appropriate medical
 judgment, they may jeopardize the participant and may require medical or surgical
 intervention to prevent one of the outcomes listed in this definition. Examples of such
 medical events include allergic bronchospasm requiring intensive treatment in an
 emergency room or at home, or blood dyscrasias or convulsions that do not result in
 inpatient hospitalization.

12.1.6. Severity Criteria

An assessment of severity grade will be made using NCI CTCAE v5.0. The CTCAE are published standardized definitions for AEs to describe the severity of laboratory and organ toxicity for patients receiving cancer therapy. The investigator should use clinical judgment in assessing the severity of events not directly experienced by the participant (eg, laboratory abnormalities).

For events not contained in CTCAE, the investigator may assign intensity according to the following generic CTCAE grading scale:

- Grade 1 = Mild; asymptomatic or mild symptoms, clinical or diagnostic observations only; intervention not indicated.
- Grade 2 = Moderate; minimal, local or noninvasive intervention indicated; limiting age-appropriate instrumental activities of daily living (ADL).
- Grade 3 = Severe or medically significant but not immediately life-threatening; hospitalization or prolongation of hospitalization indicated; disabling; limiting self care ADL.
- Grade 4 = Life-threatening consequences; urgent intervention indicated.
- Grade 5 = Death related to AE.

12.2. Adverse Event Collection and Documentation

12.2.1. All Adverse Events

All participants who receive at least one dose of study drug will be considered evaluable for safety. AEs will be determined based on signs, symptoms, physical examination findings, and/or laboratory test results from enrolled participants as appropriate.

All AEs, whether serious or non-serious, will be reported from the time participant consent is obtained through the EOTV or 30 days following the last dose of study drug or until the start of subsequent anticancer therapy (whichever occurs first). The investigator should follow and provide updates for all AEs until clinical recovery is complete, laboratory values return to normal, the participant stabilizes, or death occurs to ensure the safety of the participants.

Both protocol-related AEs and SAEs will be collected from the time the participant has consented to study participation. AEs and SAEs reported between the time participant consent is obtained and administration of the first dose of study drug will be captured as concurrent medical history unless the events are attributed to protocol-specified procedures. Events attributed to protocol-specified procedures will be collected on the AE eCRFs and SAE report form as appropriate.

All AEs, regardless of seriousness, severity, or presumed relationship to study drug, must be recorded using medical terminology in the source document and the eCRF. All records will need to capture:

- Duration, severity, and seriousness of each AE
- Action taken with respect to the study drug
- Investigator's attribution/causality assessment
- Event outcome

Whenever possible, diagnoses should be given when signs and symptoms are due to a common etiology (eg, cough, runny nose, sneezing, sore throat, and head congestion should be reported as "upper respiratory infection"). All treatment measures that are required for AE management must be recorded in the source document. The intensity (severity) of AEs will be assessed using NCI CTCAE v5.0 and serious events will be determined by the definition provided in Section 12.1.5 above.

Clinical Laboratory Changes: Safety laboratory assessments will be evaluated by the investigator to ensure participant safety. Laboratory tests will be graded according to NCI CTCAE v5.0. The investigator is responsible for reviewing the results of all laboratory tests as they become available:

- Laboratory values that fall outside of a clinically accepted reference range or values that differ significantly from previous values must be evaluated by the investigator for clinical significance. The investigator may repeat the laboratory test or request additional tests to verify the results of the original laboratory tests.
- A laboratory abnormality is reported as an AE if it is associated with an intervention. An intervention includes, but is not limited to, discontinuation of study drug, dose

reduction/delay, or concomitant therapy. In addition, any medical important laboratory abnormality may be reported as an AE at the discretion of the investigator. This includes laboratory abnormalities for which there are no interventions, but the abnormal value(s) suggests a disease or organ toxicity. If clinical sequelae are associated with a laboratory abnormality, the diagnosis or medical condition should be reported (eg, renal failure, hematuria) not the laboratory abnormality (eg, elevated creatinine, urine red blood cell increased).

Section 12.2.5 summarizes AE reporting to sponsor timeframes. The sponsor assumes responsibility for appropriate reporting of AEs to regulatory authorities. The sponsor will also notify the investigator of regulatory submissions, as appropriate. The investigator is responsible for notifying the appropriate IEC/IRB that approved the protocol, unless otherwise required and documented by the IEC/IRB.

For this study, the participants must be provided with a study card and instructed to carry this study card with them for the duration of the study indicating the following:

- Study number
- Statement, in the local language(s), that the participant is enrolled in a clinical study
- Investigator's name and 24-hour contact telephone number
- Site number
- Participant number

PD under study is an anticipated occurrence and is part of the efficacy objectives of this study. PD is not an AE. However, any medical event or condition that results from PD, if untoward, should be reported as an AE.

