4. INVESTIGATIONAL PLAN

4.1. Overall Study Design and Plan

This study is a Phase 1/2, first-in-human, open-label, dose-escalation and expansion study designed to characterize the safety, tolerability, PK, immunogenicity, and preliminary antitumor activity of IMGC936.

Participants with unresectable, relapsed or refractory, locally advanced or metastatic non-squamous NSCLC, TNBC, CRC, gastroesophageal cancer, or pancreatic cancer will be enrolled globally in approximately 26 centers.

Up to a maximum of 345 participants will be enrolled in the study if all expansion cohorts are fully enrolled.

Each cycle is 21 days for Schedule A and 28 days for Schedule B. IMGC936 is administered via IV infusion at the assigned dose for each cohort. Infusion duration will vary depending on dose and participant tolerability.

Participants may continue on study drug until disease progression, AE requiring discontinuation, withdrawal of consent, physician decision, or other discontinuation criteria are met (Section 5.4).

Participants will be followed for safety throughout the study. Any participant who discontinues study drug should return to the study site for an end of treatment visit (EOTV). The visit should be performed within 30 days following last dose of study drug whenever possible.

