9.14. End of Treatment Visit

A list of evaluations at the EOTV is provided in Appendix 1 and Appendix 2. The EOTV should be performed after the participant has met study drug discontinuation criteria (Section 5.4). The visit should be performed within 30 days following last dose of study drug whenever possible. Tumor assessments are performed at EOTV except if prior assessment was \leq 30 days of EOTV and results are available for RECIST v1.1 assessment.

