9.15.1. Safety

Ongoing TEAEs will be followed until the event has resolved to baseline grade, the event is assessed by the investigator as stable, initiation of another anticancer therapy, withdrawal of consent, LTFU, or death. The investigator should follow and provide updates for all AEs until clinical recovery is complete, laboratory values return to normal, the participant stabilizes, or death occurs to ensure the safety of the participants.

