12.2.2. Serious Adverse Events

All SAEs occurring during the study must be reported to the sponsor.

After 30 days following the last dose of study drug administration, if an investigator becomes aware of an SAE that they suspect is related to study drug, the investigator should report the event to the sponsor.

Within 24 hours of becoming aware of an SAE, the investigator should provide a completed SAE report form, via email or fax, to the sponsor. Upon receipt of follow-up information pertaining to an SAE, a follow-up SAE report form should be submitted to the sponsor within 24 hours of becoming aware of the follow-up information. All SAEs should be entered into the eCRFs within 5 calendar days of the site's awareness.

The investigator must follow all SAEs until resolution and record the date of resolution. Resolution of an event is defined as the return to pre-treatment status or stabilization of the condition with the expectation that it will remain chronic.

All SAEs that have not resolved by the end of the study, or that have not resolved upon discontinuation of the participant from the study, must be followed until any of the following occurs:

ImmunoGen, Inc ment 3 29 March 2022

IMGC936 Clinical Study Protocol: IMGC936-0901 Amendment 3

- The event resolves
- The event stabilizes
- The event returns to baseline, if a baseline value/status is available
- It becomes unlikely that any additional information can be obtained (participant or health care practitioner refusal to provide additional information, LTFU after demonstration of due diligence with follow-up efforts)

Any event requiring hospitalization (or prolongation of hospitalization) that occurs during enrollment in a study must be reported as an SAE, except hospitalizations for the following:

- A standard hospitalization for administration of study drug therapy will not be reported as an SAE
- A procedure for protocol/disease-related investigations (eg, surgery, scans, endoscopy, sampling for laboratory tests, bone marrow sampling, PK or biomarker blood sampling)
- Hospitalizations not intended to treat an acute illness or AE (eg, social reasons such as pending placement in long-term care or hospice facility)
- Surgery or procedure planned before entry into the study (must be documented in the eCRF)

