#### 7. SAFETY ANALYSES

The safety analyses will be performed on the Safety population. The assessments/events up to 30 days (inclusive) of the last dose of study drug or prior to the start of a new anti-cancer treatment, whichever occurs first, will be analyzed, unless otherwise stated. Baseline is defined as the last non-missing observed measurement prior to the first dose of study drug.

Unless otherwise stated, summaries of safety data will be presented for each dose level of IMGC936, combined RP2P dose (6mg/kg) as well as for overall of all patients in the Safety population.

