## 7.2. Adverse Events (AEs)

AEs will be documented on the AE eCRF and monitored continuously throughout the study from the time of informed consent until 30 days after the patient's last study drug or until the event has resolved, stabilized, or returned to baseline. AEs attributed to study procedures, including those events that occur prior to the first dose, should also be documented on the AE eCRF.

AE data are available to ImmunoGen from 2 sources, the eCRFs and the serious adverse event (SAE) forms. While reconciliation will be performed, the production of data summaries and listings will be based on the data collected on the eCRF.

Pre-treatment AEs are defined as AEs with an onset date prior to the first dose of study drug. TEAEs are defined as AEs with an onset date on or after the first dose of study drug, and within 30 days of the last dose of study drug or prior to the start of a new anti-cancer treatment, whichever occurs first. Medical history conditions that exist before the initiation of study drug but worsen in severity during the study will also be recorded on the AE eCRF as an AE and will be included as treatment-emergent in the summary tables and listings.

The adverse events will be coded using MedDRA, associating lower-level terms with PT and SOC by the primary hierarchy. The tables will display the counts and percentages of patients who reported at least 1 TEAE in each SOC represented in the AE data. Within each SOC, the tables will display the counts and percentages of patients reporting at least 1 TEAE as designated by the PT.

AEs are graded using Common Terminology Criteria for Adverse Events (CTCAE) Version 5.0. AE summaries may include summaries for all AEs and by the maximum CTCAE grade for the item being summarized (ie, SOC or PT). In these cases, the outputs will include a row for All Grades as well as rows for the 5 potential CTCAE grades, Grade 1 (Mild), Grade 2 (Moderate), Grade 3 (Severe), Grade 4 (Life threatening or disabling), or Grade 5 (Death). AEs missing a severity grade will not be included in the Grade 1-5 rows of the tables. An AE reported by a patient more than once will be represented in the most severe category.

Ocular AEs including blurred vision events and grouped keratopathy events will be analyzed for outcome, resolution, time to onset and time to resolution. Patients at 6mg/kg who administered different prophylactic eye drops will be further analyzed.

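### The protocol can end AE collection at the End of Treatment Visit, while the SAP counts new events to Day 30 after last dose with no such limit

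*Protocol*

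**What the plan says.** **Protocol, collection.** Section 12.2.1 reports all AEs, serious and non-serious alike, from consent "through the EOTV or 30 days following the last dose of study drug or until the start of subsequent anticancer therapy (whichever occurs first". The Synopsis and the opening of Section 12 use the same three end points and the same earliest-of rule.

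**Protocol, timing of the visit.** Section 4.1 says of the EOTV: "The visit should be performed within 30 days following last dose of study drug whenever possible". Section 9.14 ties it to stopping treatment: "The EOTV should be performed after the participant has met study drug discontinuation criteria (Section 5.4". Neither sets an earliest day.

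**Protocol, after the visit.** Section 9.15.1 provides that "Ongoing TEAEs will be followed until the event has resolved to baseline grade" or another stopping point is reached. Section 12.2.2 adds that "All SAEs occurring during the study must be reported to the sponsor", and its narrower rule for suspected-related SAEs starts only after Day 30.

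**SAP.** Section 7 analyses "The assessments/events up to 30 days (inclusive) of the last dose of study drug", or up to a new anti-cancer treatment if that comes first. Section 7.2 defines a TEAE by onset on or after first dose and "within 30 days of the last dose of study drug or prior to the start of a new anti-cancer treatment, whichever occurs first". It also describes AEs as documented and monitored "from the time of informed consent until 30 days after the patient's last study drug or until the event has resolved". The EOTV is not an end point in any of these statements.

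**The concern.** The SAP describes an observation period that the protocol does not guarantee. Both documents stop at new anticancer therapy, so the EOTV is the only point of difference. When the EOTV falls before Day 30, the protocol's 30-day limit has no effect, yet the safety tables will be read as if every participant without new therapy had been observed for the full 30 days.

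AE incidence is part of the primary endpoint in escalation and a secondary endpoint in expansion. The SAP presents safety by dose level and analyses time to onset of ocular events. If the period actually observed varies with the day of the EOTV, those summaries mix participants with different follow-up, and nothing in the tables shows it.

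**Working it through.** The plan gives no figure to reproduce. The check compares definitions, followed by simple arithmetic on the gap.

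**Step 1. End of window, side by side.**

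| Source | EOTV | Day 30 | New anticancer therapy |
|---|---|---|---|
| Protocol Synopsis, 12, 12.2.1 | ends collection | ends collection | ends collection |
| SAP 7, and TEAE definition in 7.2 | not mentioned | ends window | ends window |

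The protocol takes the earliest of the three. An EOTV on day *d* after last dose, with *d* < 30 and no new therapy, therefore ends collection on day *d*, while the SAP window stays open to Day 30.

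**Step 2. Does another provision cover days *d* to 30?**
- Section 9.15.1 follows TEAEs that are already ongoing. It does not provide for collecting new onsets.
- The footnotes to the follow-up column in Appendices 1 and 2 specify tumor assessments only.
- Section 4.6.2 names a Safety Follow-up Visit, but Sections 9.14 and 9.15 and the schedule footnotes describe no such visit.
- Section 12.2.2 appears to cover SAEs to Day 30. That conflicts with Section 12.2.1, which applies its cut-off to serious events too.
- Deaths have other routes: the end-of-study form (4.6.2, 6.5), a case report form page for death (12.2.2), and PFS (14.7.3).

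What remains uncovered is mainly new-onset, non-serious events.

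**Step 3. Size of the gap.** Uncovered share = (30 − *d*)/30. The documents do not give *d*, so it is assumed over a range.

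| EOTV day *d* | Days uncovered | Share |
|---|---|---|
| 7 | 23 | 23/30 = 77% |
| 14 | 16 | 16/30 = 53% |
| 21 | 9 | 9/30 = 30% |
| 28 | 2 | 2/30 = 7% |
| 30 | 0 | 0% |

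**Step 4. Effect on an observed risk (illustration only).** Assume a constant onset rate, a true risk *R* of a given event over the 30 days, and every EOTV on day *d*. Observed risk = 1 − (1 − *R*)^(*d*/30). With *R* = 20%, an EOTV on Day 7, 14, 21 or 28 gives 5.1%, 9.9%, 14.5% or 18.8%. With *R* = 10%, it gives 2.4%, 4.8%, 7.1% or 9.4%. Both *R* and *d* are assumptions. The calculation covers only the post-dose window. Events during treatment are collected either way, so overall TEAE incidence is affected less than these figures suggest.

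**The case against.** The strongest reply is that the documents show inconsistent wording and not an established loss of data. The schema note in protocol Section 1.1 gives the same window without the earliest-of rule. The AE-assessment row in both schedules reads as continuous, although its column span is unclear in the extracted tables. The SAP itself describes monitoring to Day 30. Some sites may therefore already collect to Day 30. This stands, and it rules out any claim that events have been lost. It does not remove the defect, because sites that read the rule differently will ascertain differently.

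The gap may also often be small. On Schedule A, dosing is every 3 weeks and scans every 6, so a scan falls about 42 − 21 = 21 days after the last dose, or 14 to 28 days with the ±7-day window. A Day 7 EOTV is untypical for progression found that way. The EOTV is also due within 30 days only where possible, so some visits will be late and the 30-day limit will then apply. Both points stand, which is why the range runs to Day 30.

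A reader might infer three stronger conclusions that the documents do not support:
- *SAEs and deaths are lost.* Section 12.2.2 and the separate recording of deaths point the other way.
- *The loss is greatest in participants who stop for toxicity.* Nothing shows this. Several toxicity rules (Table 7, Sections 7.7.1 and 7.7.2) allow holds of 21 to 42 days before discontinuation, which would put the EOTV late. Events requiring an immediate stop are exceptions.
- *The escalation decisions are compromised.* DLTs have their own window, Cycle 1 Day 21 or Day 28 (Section 4.2).

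Finally, ending the SAP window at the EOTV would also remove the mismatch. That is true, but it shortens safety observation and would have to be reported as a limitation.

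**Conclusion.** Wrong as written. The protocol's collection rule and the SAP's analysis window have different end points, and no other provision clearly closes the gap for new, non-serious AEs after an early EOTV. The uncovered share of the 30 days ranges from 77% for an EOTV on Day 7 to 0% on Day 30. It depends entirely on the timing of the EOTV, which the documents do not give. The conclusion assumes that sites apply the earliest-of rule literally and that no new anticancer therapy starts before Day 30. Sections 12.2.1 and 12.2.2 also contradict each other on SAEs.

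The consequence is a safety summary that may understate late non-serious events and overstate the period observed. The safety analyses are descriptive (SAP Sections 4.9 and 4.10 plan no hypothesis test), so the defect should be corrected but does not invalidate the trial.

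**What to change.** 1. In the protocol Synopsis, Section 12 and Section 12.2.1, remove the EOTV as an end point. AEs are then collected to 30 days after last dose or the start of subsequent anticancer therapy, whichever is earlier. Add a Day 30 telephone AE check when the EOTV is earlier.
2. Give the schema note in Section 1.1 the same window, and reconcile Section 12.2.2 with Section 12.2.1 on SAEs.
3. Define the Safety Follow-up Visit in Section 4.6.2, or remove it.
4. A telephone call cannot supply laboratory values. SAP Sections 7 and 7.3 should state that laboratory observation ends at the last sample, normally the EOTV.

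With these changes the AE windows match and the uncovered time is 0 days. If the protocol cannot be amended, the SAP should state the window actually observed and report the shortfall as a limitation.

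The cost is protocol and SAP wording, one telephone contact for each participant with an early EOTV, and possibly slightly higher reported AE rates.

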12.2.2. Serious Adverse Events

All SAEs occurring during the study must be reported to the sponsor.

After 30 days following the last dose of study drug administration, if an investigator becomes aware of an SAE that they suspect is related to study drug, the investigator should report the event to the sponsor.

Within 24 hours of becoming aware of an SAE, the investigator should provide a completed SAE report form, via email or fax, to the sponsor. Upon receipt of follow-up information pertaining to an SAE, a follow-up SAE report form should be submitted to the sponsor within 24 hours of becoming aware of the follow-up information. All SAEs should be entered into the eCRFs within 5 calendar days of the site's awareness.

The investigator must follow all SAEs until resolution and record the date of resolution. Resolution of an event is defined as the return to pre-treatment status or stabilization of the condition with the expectation that it will remain chronic.

All SAEs that have not resolved by the end of the study, or that have not resolved upon discontinuation of the participant from the study, must be followed until any of the following occurs:

ImmunoGen, Inc ment 3 29 March 2022

IMGC936 Clinical Study Protocol: IMGC936-0901 Amendment 3

- The event resolves
- The event stabilizes
- The event returns to baseline, if a baseline value/status is available
- It becomes unlikely that any additional information can be obtained (participant or health care practitioner refusal to provide additional information, LTFU after demonstration of due diligence with follow-up efforts)

Any event requiring hospitalization (or prolongation of hospitalization) that occurs during enrollment in a study must be reported as an SAE, except hospitalizations for the following:

- A standard hospitalization for administration of study drug therapy will not be reported as an SAE
- A procedure for protocol/disease-related investigations (eg, surgery, scans, endoscopy, sampling for laboratory tests, bone marrow sampling, PK or biomarker blood sampling)
- Hospitalizations not intended to treat an acute illness or AE (eg, social reasons such as pending placement in long-term care or hospice facility)
- Surgery or procedure planned before entry into the study (must be documented in the eCRF)

PD should not be reported as an SAE term; however, any serious medical event/condition that results from progression of underlying disease, if untoward, should be reported as the SAE. The applicable protocol case report form page(s) pertaining to death should be appropriately completed, however, as disease progression. Death should not be reported as an SAE term. Death is an outcome of a specific SAE term. In exceptional cases, "death of unknown cause" may be used as an event term until the cause of death has been determined. If an autopsy was performed, the autopsy report should be provided.

